6.6.1 Unscheduled visit

An unscheduled visit may be made at any time throughout the clinical trial at the request of the patient or at the discretion of the principal investigator and/or the investigating physician.

The date and reason for the unscheduled visit will be recorded in the primary medical record and individual registration form. The data of the unscheduled visit will be registered in the primary medical documentation and the individual registration form of the patient.

The reasons for an unscheduled visit may be:

• Occurrence of AE/AR or observation of the course of AE/AR;

• Assessment of the dynamics of the patient's condition;

· Assessment of the dynamics of instrumental survey indicators;

• Changes in concomitant therapy;

- Another significant reason (must be specified).
- The following clinical trial procedures will be performed during the unscheduled visit:

· Physical exploring;

- Measurement of vital signs (body temperature, heart rate, blood pressure, respiratory rate); • Assessment of the presence and severity of AE/AR.

Additional clinical trial procedures during an unscheduled visit may include any of the clinical trial procedures that will be decided on a case-by-case basis by the investigating physician in consultation with the Sponsor.

Diet and fluid intake 6.7

Patients should follow a regular diet, fluid intake and physical activity throughout the study period.

Patients are advised to refrain from food and drink that may impair kidney and liver function (eg., alcoholic beverages, high-fat foods, fried foods in large quantities). When receiving blood samples - the last meal the day before at least 12 hours. Blood sampling is also performed on an empty stomach.

6.8 Mode of physical activity

Throughout the study period, patients should adhere to physiologically normal sleep and activity, without increased physical activity and exercise.

7 INFORMATION ON MEDICINAL PRODUCTS USED IN CLINICAL TRIAL

7.1 Study drug

Name of the medicinal product: BIOVEN *Composition*

active substance: Human normal immunoglobulin for intravenous administration;

1 ml of the drug contains normal human immunoglobulin 0.1 g (including immunoglobulin G (IgG) at least 95%);

Excipients: glycine (amino acetic acid); water for injections.

Pharmacotherapeutic group: Human normal immunoglobulin for intravenous administration. ATC code J06B A02

Dosage form: solution for infusion.

The product is an immunologically active protein fraction (ratio of immunoglobulin G subclasses in the drug product: IgG1: 65.6 %, IgG2: 22.1 %, IgG3: 10.8 %, IgG4: 1.5 %) max. content of immunoglobulin A in the drug product is 50 µg/ml.

Active components of the product are antibodies that have a specific activity against different pathogenic agents such as viruses and bacteria including hepatitis A and B, herpes, chicken pox, influenza, measles, parotitis, poliomyelitis, German measles, whooping cough, staphylococcus, Escherichia coli and pneumococcus. It also has a non-specific activity to increase organism resistance.

The drug product is a native immunoglobulin G and retains all biological properties: complement activation; effector and opsonocytophagic function.

The product is an immunologically active protein fraction extracted from human blood serum or plasma and screened negative for antibodies to HIV-1, HIV-2, hepatitis C virus and surface antigen of hepatitis B virus, purified and concentrated by use of the fractionation method with water-alcohol precipitating agent that passed the phase of virus inactivation by use of solvent-detergent method and nanofiltration method.

7.2 Circulation of the study drug

Manufacturing, packaging and labeling of the investigated drug is carried out by the Sponsor - the manufacturer of the drug LLC "BIOPHARMA PLASMA".

The study drug is provided to the clinical base by the Sponsor in the amount required for this study. Transfer of the drug is confirmed by the act of transfer, which indicates: the number of drugs, batch numbers, expiration date, date of transfer. The act is signed by the Sponsor and the Responsible Researcher of the clinical base.

On a clinical basis, the study drug should be placed in an individual clearly marked package for each patient. The drug should be stored in a dry, protected from light at a temperature of 2-8 degrees Celsius. The drug should be stored indoors, accessible only to the investigating physician or members of the research team to whom the responsible researcher has delegated the appropriate authority.

The person authorized by the Responsible Researcher keeps a journal of the study drug.

The journal, at each delivery of the drug to the patient, indicates: the name of the drug, date of issue, quantity, as well as the patient's number in this clinical trial and the patient's initials, the researcher's signature.

| Bioven | Page 58 |
|----------------------------|--------------------------------|
| Trial Code: 2021-BV-ITP-BP | Version 1.4 from July 03, 2023 |

The packaging of the used drug is stored for a period determined by the Sponsor. Unused drugs are returned to the Sponsor, which is confirmed by the act of transfer.

To allow for re-testing if required by the Authority, the Study Sponsor must maintain a sufficient number of specimens of investigational medicinal products for one year after the expiration date or for two years after completion of the study (whichever is longer).

7.3 Labeling of the study drug

The study drug should be marked with the following symbols and fields:

- mark "Only for clinical trials";
- drug name;
- composition, including the content of active substances in the vial;
- method of administration;
- manufacturer's name, location, telephone number;
- serial number;
- expiration date;
- storage conditions;
- clinical trial code;
- center code;
- patient code.

The serial number indicated on the label must correspond to the batch number indicated in the quality certificate of BIOPHARMA PLASMA LLC.

7.4 The order of administration of the study drug

The introduction of SD will be carried out in a hospital or day hospital under the supervision of a investigator. The primary documentation and IRF record the time of drug administration, the occurrence of possible side effects.

As part of this clinical study, patients will receive the drug Bioven, 10% infusion solution, manufactured by "Biopharma Plasma" LLC at a dose of 0.8-1.0 g/kg1 time per day for 2 consecutive days (course dose 1.6-2.0 g / kg). Allowed repeat course at same dosage in period 14-28 days from first infusion, if required.

Bioven should be administered intravenously at an initial rate of 0.5 - 1.0 ml / kg body weight / h for 30 minutes. In the absence of any undesirable side effects, the rate of administration can be gradually increased (recommended increase by 0.5 - 1.5 ml / kg body weight / h every 10 minutes). According to clinical studies, the maximum rate of administration is 8.5 ml / kg body weight/hour.

The study drug is administered only in a hospital setting in accordance with the rules of asepsis.

The solution should be at room temperature before use. Turbid and sedimentary solutions are not used. A separate infusion system should be used for drug administration. When administering the drug should take into account the information provided in the instructions for medical use in the relevant sections: *Features of application, Special safety measures, Contraindications, Interaction with other drugs*, etc. Including but not limited to, measures to control the state of the coagulation system, hydration levels, kidney function and more.

According to the section "Special features of use", and as described in section 2.5 "Specifics of use" of this protocol for patients at risk of thrombosis, the introduction of immunoglobulin drugs in minimal doses and with a minimum infusion rate.

| Bioven | Page 59 |
|----------------------------|--------------------------------|
| Trial Code: 2021-BV-ITP-BP | Version 1.4 from July 03, 2023 |

Before using the drug, make sure the patient's level of hydration is adequate. Patients at risk of high viscosity should be monitored for thrombosis symptoms and blood viscosity assessed. Patients in this study may receive concomitant therapy, which is used to treat comorbidities and vital signs.

The route of administration and dosage doesn't exceed the maximum single and course doses that can be used in the treatment of patients, according to the approved Instructions for medical use of the drug Bioven. They fully meet the requirements for the finished medicinal product, which are strictly regulated by the European Pharmacopoeia (monograph Eur. Ph.0918), the State Pharmacopoeia of Ukraine, and are within the limits set out in the Guideline on core SmPC for human normal immunoglobulin for intravenous administration (IVIg) EMA / CHMP / BPWP / 94038/2007 Rev. 5 June 28, 2018.

7.5 Concomitant therapy is allowed.

The use of any drugs other than those listed in section 7.4 is permitted. Patients should refrain from unprotected sexual intercourse throughout the study. Within 30 days of completion, study participants with preserved reproductive potential should use effective barrier contraception. The purpose of barrier contraception is to prevent sexually transmitted diseases, including HIV, HBV, HCV.

Effective methods of contraception include:

• Full maintenance;

• Condom or double barrier method.

7.6 Concomitant therapy is prohibited.

The following drugs are prohibited during the participation of patients in a clinical trial:

- 1. Corticosteroids are allowed only if the patient is taking long-term stable doses at least 2 weeks before screening;
- The dose of corticosteroids or other immunosuppressant should remain unchanged for up to 31 days;
- 3. If patients have been treated with cyclophosphamide, azathioprine or attenuated androgens, the treatment regimen should be stable for at least 2 months before Day 0;
- 4. Monoclonal antibodies;
- 5. Avatrombopag;
- 6. Antiplatelet agents;
- 7. Anticoagulants.

8 EVALUATION OF EFFICIENCY

8.1 Primary efficacy endpoint:

Part (percent) of patients with response (R).

R is determined according to the following criteria:

- Patients with R: platelets count $> 30x10^{9}/L$ and at least a two-fold increase from the baseline count. This must be confirmed by at least 2 blood tests at least 7 days apart, and the absence of bleeding;

The primary efficacy variable is achievement of R during the study (yes/no).

8.2 Secondary efficiency endpoints

Part (percent) of patients with a complete response (CR).

CR is determined according to the following criteria:

- Patients with CR: platelets count > 100 x 10^{9} /L, which is confirmed by 2 blood tests performed at least 7 days apart and the absence of bleeding;

Part (percent) of patients with no response (NR).

NR is determined according to the following criteria:

- Patients with NR: platelet count $< 30 \times 10^{9}$ /L or less than two-fold increase of baseline platelet count. This must be confirmed by at least 2 blood tests performed approximately 1 day apart, or the presence of bleeding;

Part (percent) of patients with loss of response (loss of R).

Loss R is determined according to the following criteria:

- Patients with loss R: a decrease platelet count < 30×10^9 /L or less than two-fold increase of baseline platelet count, or the occurrence of bleeding. Platelet counts confirmed at least 2 blood tests performed approximately 1 day apart.

Part (percent) of patients with loss of complete response (loss of CR).

CR loss is determined according to the following criteria:

- Patients with loss of CR: decrease platelet count < 100 x $10^9/L$, or the occurrence of bleeding. Platelet counts confirmed at least 2 blood tests performed approximately 1 day apart.

Time (in days) from treatment start to onset of a response (R); Time (in days) from treatment start to onset of a complete response (CR); Duration (in days) of response (R); Duration (in days) of complete response (CR);

Secondary efficacy endpoints are transformed into corresponding efficacy variables

Safety

- Frequency (percent) of adverse events

- Frequency (percent) of serious adverse events

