Bioven should be administered intravenously dropwise at the initial rate of 0.5-1.0 ml/kg of body weight/hour for 30 minutes. If no adverse reactions occur, the rate of administration may be gradually increased (it is recommended to increase by 0.5-1.5 ml/kg of body weight/hour every 10 min). According to the data from clinical studies the maximum rate of administration is 8.5 ml/kg of body weight/hour.

The study drug is administered only in hospital environment while observing the rules of aseptic. The solution should be of room temperature before use. Cloudy solutions and those containing sediment are not used. For the administration of the drug, it is necessary to use a separate infusion system.

When administering the drug, it is necessary to consider the information specified in the relevant sections of the instructions for medical use: administration details, special safety measures, contraindications, interaction with other medicinal products, etc.

Patients participating in this study may receive concomitant therapy, which is used for the treatment of comorbidities and life-threatening conditions.

It is allowed to use glucocorticoids in a stable dose for at least 2 weeks before starting treatment with the test drug. The need to increase the dose of corticosteroids during the study is considered as ineffective use of the study drug.

Duration of treatment:

The duration of treatment with the study drug for each patient is no less 2 days. The total period of stay in the study is 4 weeks.

Efficacy and safety endpoints: Efficacy:

Primary efficacy endpoint:

| Bioven | |
|----------------------------|--|
| Trial Code: 2021-BV-ITP-BP | |

Page 11 Version 1.4 from July 03, 2023,

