After the informed consent form is signed, the screening tests are performed and the compliance with the inclusion / non-inclusion criteria is evaluated. The patient who passed the screening tests is enrolled in the study.¹

Clinical phase

Patients enrolled in the study receive Bioven at a dose of:

0.8-1.0 g / kg intravenously once a day for 2 consecutive days, the course dose is 1.6-2.0 g / kg. Allowed repeat course at same dosage in period 14-28 days from first infusion, if required.

The CRF records the time of administration of the study drug, the occurrence of possible adverse events.

Prescribed therapy and diagnostic results are recorded in the CRF based on the primary documentation.

Data are entered into the CRF according to the patient management plan.

Follow-up phase and completion of the study

This stage lasts for 4 weeks after the last administration of the drug (possible repeat course is not considered).

In all patients, the platelet count will be determined 48 hours after the start of the first administration of the study drug, on the 7th (\pm 1 day), 14th (\pm 2 days), 21st (\pm 3 days), 28th (+ 1-3 days) days after the start of therapy.

The results of the study are evaluated by endpoints.

Phase-by-phase breakdown and breakdown of visits are detailed in Section 6.4 "Tabulated schedule of events". Information is entered into the CRF after each visit, according to the "Schedule of study events".

The decision on any examinations and diagnostic procedures in routine clinical practice is made and controlled by professionals.

Blood sampling for platelet count is performed 6 times:

- at the screening phase;
- 48 (\pm 3) hours after the start of study drug administration;
- on the 7th (± 1) day from the start of study drug administration;
- on the 14th (± 2) day from the start of study drug administration;
- on the 21st (± 3) day from the start of study drug administration;
- on the 28th (+ 1-3) day from the start of study drug administration.

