6.3 Stage of follow-up and completion

The stage lasts from the last administration of the study drug and for 4 weeks.

The procedures are performed according to the schedule of procedures (Section 6.4, Table 1). If a decrease in platelet count $< 30 \times 109/L$ is detected, an additional blood test with platelet count by Fonio is performed one day after the visit.

Face-to-face or telephone/video visits are made to assess the patient's condition. The patient visits the blood collection point for laboratory testing. The investigator fills in all information about the patient's condition and examination results in the IRF.

| Bioven | |
|----------------------------|-------------|
| Trial Code: 2021-BV-ITP-BP | Version 1.2 |

6.4 Schedule of study procedures in tabular form Table 1. Schedule of study procedures.

| Visits | Visits 1 | Vi | sits 2 (госпіт | алізація) | Visits 3 | PLT control | Visits 4 | PLT control | Visits 5 | PLT control | Visits 6 | PLT contro |
|--|------------------------|-----------|----------------|-----------|-----------|----------------|-----------|----------------|-----------|----------------|-----------|---------------|
| Study stage | Screening ² | IMP admin | . IMP admin | Follow-up | Follow-up | every | Follow-up | every | Follow-up | every | Follow-up | every |
| Day relative to the first administration of the drug/Injection | Day (-14 -1) | Day 0 | Day +1 | Day +2 | Day +7 | day* | Day +14 | day* | Day +21 | day* | Day +28 | day* |
| Signing the Informed Consent Form | • | | | | | | | | | | | |
| Collection of demographics data | • | | | | | | | | | | | |
| Collection of anthropometric data, body weight ³ | • | • | • | | | | | | | | | |
| Collection of medical history ⁴ | • | | | | | | | | | | | |
| Objective physical examination 5 | • | • | • | • | • | | • | | • | | • | |
| Measurement of vital signs 6 | • | • | • | • | • | | • | | • | | • | |
| ECG in 12 leads; | • | | | | | | | | | | | |
| Coombs Direct Test (Antiglobulin Test)* | • | | | • | * | | * | | * | | • | |
| Determination of the level of total Ig G in the blood (g/l) | • | | | • | • | | • | | • | | • | |
| General blood test ⁷ | • | | | • | • | * | • | * | • | * | • | * |
| Biochemical blood test 8 | • | | | | | | | | | | • | |
| Blood test for blood group and Rh factor | • | | | | | | | | | | | |
| Coagulogram (PTI, APTT, fibrinogen) | • | | | | | | | | | | | |
| General urine analysis ⁹ | • | | | | | | | | | | | |

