The variable is analyzed for patients who achieved a response (R) during the study.

Non-response (NR) during the study.

NR is determined according to the criteria *:

- Patients with NR: $patient count < 30 \times 10^{9}$ /L or less than two-fold increase of baseline platelet count. This must be confirmed by at least 2 blood tests performed approximately 1 day apart, or the presence of bleeding;

The categories of the variable will be defined as "Yes" or "No" respectively.

The variable is analyzed relative to the total number of patients included in the analysis.

Loss of response (loss of R).

R loss is determined according to the criteria *:

 Patients with loss R: a decrease platelet count < 30 x 10⁹/L or less than two-fold increase of baseline platelet count, or the occurrence of bleeding. Platelet counts confirmed at least 2 blood tests performed approximately 1 day apart.

The categories of the variable will be defined as "Yes" or "No" respectively.

The variable is analyzed for patients who achieved a response (R) during the study.

Loss of complete response (loss of CR).

CR loss is determined according to the criteria *:

Patients with loss of CR: decrease platelet count $< 100 \times 10^9$ /L, or the occurrence of bleeding. Platelet counts confirmed at least 2 blood tests performed approximately 1 day apart.

The categories of the variable will be defined as "Yes" or "No" respectively. The variable is analyzed for patients who achieved a complete response (CR) during the study.

Time (in days) from treatment start to onset of a response (R);

A Kaplan Meier curve will be constructed and the median time to event will be estimated. The variable is analyzed for patients who achieved a response (R) during the study.

Time (in days) from treatment start to onset of a complete response (CR);

A Kaplan Meier curve will be constructed and the median time to event will be estimated. The variable is analyzed for patients who achieved a complete response (CR) during the study.

Duration (in days) of response (R);

A Kaplan Meier curve will be constructed and the median time to event will be estimated. The variable is analyzed for patients who achieved a response (R) during the study.

Duration (in days) of complete response (CR);

A Kaplan Meier curve will be constructed and the median time to event will be estimated. The variable is analyzed for patients who achieved a complete response (CR) during the study.

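### Loss and duration of R have no scoring rule for a responder who receives the permitted repeat course before loss is confirmed

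*Combined protocol and SAP*

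**What the plan says.** On retreatment, Section 7.4 states: "Allowed repeat course at same dosage in period 14-28 days from first infusion, if required". The Synopsis and Section 6.2 say the same. None of them gives a trigger for the repeat course.

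On loss of R, Section 8.2 takes a count below 30 x 10^9/L, "or less than two-fold increase of baseline platelet count, or the occurrence of bleeding". The platelet criteria carry a confirmation requirement: "Platelet counts confirmed at least 2 blood tests performed approximately 1 day apart". Bleeding needs no confirming count.

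On the confirming test, Section 6.3 says that when a count below 30 x 10^9/L is found, "an additional blood test with platelet count by Fonio is performed one day after the visit". Section 6.5.10 uses the same threshold.

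On analysis, Section 10.3.3 restricts loss and duration of R to responders: "The variable is analyzed for patients who achieved a response (R) during the study". For duration it adds: "A Kaplan Meier curve will be constructed and the median time to event will be estimated". It defines no event date, censoring rule or handling of a repeat course.

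The repeat course does not appear in Sections 8, 10.3.3, 10.3.6 or 10.4. The Synopsis remark "possible repeat course is not considered" belongs to the sentence on how long follow-up lasts. By contrast, a steroid increase does have a scoring rule in the Synopsis: "The need to increase the dose of corticosteroids during the study is considered as ineffective use of the study drug". Section 4.3 has a similar rule.

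**The concern.** Loss and duration of R are meant to describe how well the response to one course of 1.6-2.0 g/kg holds. A second course at the same dosage can remove the evidence of relapse before the two-count rule is met. Later counts then reflect the second course, but the plan credits them to the original response. The patients affected are those whose response may be failing, so the error runs in one direction: loss is understated and duration overstated. The same applies to loss and duration of CR. In an open-label, single-arm study, leaving this unspecified also means that the scoring would be settled after the counts are known.

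**Working it through.** The plan gives no expected figure for loss or duration of R, so the check is mainly a reading of the definitions against the visit schedule.

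**1. Patient numbers.** Section 10.2 gives n = (1.96 + 1.28)² × 0.78 × 0.22 / 0.25² = 28.82, so 29, which reproduces. With 20% dropout, 29 / 0.8 = 36.25; the plan states 36. Section 4.1 gives 40. These serve below only as possible denominators.

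**2. When loss can be seen on scheduled visits.** R needs two counts at least 7 days apart (Section 8.1). The 48-hour count and Visit 3 (Day 6-8) are 4-6 days apart, which is too close. R is therefore first confirmed at Visit 4 (Day 12-16). A scheduled relapse of a confirmed responder first appears at Visit 5 (Day 18-24), which lies wholly inside the Day 14-28 window for a repeat course. Visit 6 lies inside it only if held by Day 28. The Synopsis puts Visit 6 at Day 28 plus 1-3 days and Section 6.2 at Day 30 ± 3.

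**3. How each case is scored as the text stands.**

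| Responder at or after Visit 4 | Scoring under Section 8.2 | Affected? |
|---|---|---|
| Bleeding | Loss at once | No |
| Count <30, next-day count also low | Loss confirmed | No |
| Count <30, repeat infusion, next-day count at least 30 and at least twice baseline | Loss unconfirmed, R continues | Yes |
| Count at least 30 but below twice baseline, then retreated | No next-day count required; Visit 6 reflects the second course; R continues | Yes |
| Falling count that still meets R, then retreated | No criterion met; duration runs on under the second course | Yes |

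The fourth row can occur. Entry requires a baseline below 30. For a baseline of 25, twice baseline is 50, so a Visit 5 count of 40 meets the loss criterion without triggering the extra test.

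Extra counts are possible (Section 6.5.10, and unscheduled visits in Section 6.6.1), but nothing requires one, or requires the confirming draw to precede a repeat infusion. The schedule in Section 6.4 has platelet-control columns after Visits 3 to 6, whose footnote is not readable in the text available. The sections that state the trigger in words give only the <30 condition.

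**4. Weight of one patient.** Responders = 78% of N; shift per patient = 100 / responders.

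| N | Responders | Points per patient | Three patients |
|---|---|---|---|
| 29 | 0.78 × 29 = 22.6, about 23 | 100/23 = 4.3 | 13.0 |
| 36 | 0.78 × 36 = 28.1, about 28 | 100/28 = 3.6 | 10.7 |
| 40 | 0.78 × 40 = 31.2, about 31 | 100/31 = 3.2 | 9.7 |

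The number of affected patients is not in the documents. The three-patient column only shows scale.

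**The case against.** **The rebound path is narrow.** It needs a platelet-only relapse, a repeat infusion before the next-day draw, and a rebound past both thresholds by then. Visits 4 and 5 may be remote, with blood taken at a collection point, while infusions are given in a hospital or day hospital. This stands for the third row of the table. It does not touch the fourth and fifth rows, which need no overnight rebound.

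**A reader might infer a large, quantified bias.** Assume exponential loss after Day 14 with a median of 21 (28) days. Loss by Day 28 is then 1 − 0.5^(14/21) = 37% (1 − 0.5^(14/28) = 29%), of which 1 − 0.5^(7/21) = 21% (1 − 0.5^(7/28) = 16%) is seen at Visit 5. If 50% of the Visit 5 losses went unconfirmed through retreatment, reported loss would fall by 10 (8) points; at 25%, by 5 (4); at 10%, by about 2. The standard error with 28 responders is about 9 points. Neither the medians nor these fractions have any source in the documents, so no single figure can be put forward.

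**A reader might infer that median duration is inflated.** With 29-37% loss by Day 28, the Kaplan-Meier median is not reached under either scoring. It is the curve that shifts.

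**A reader might infer that censoring at the repeat course is plainly wrong.** The documents give no trigger for the course, and the indication in the Synopsis includes platelet correction before surgery. Some repeat courses may therefore not signal a failing response. Scoring all of them as loss is one defensible choice, with a known cost.

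**Part of the gap has another cause.** A fall from above 100 to 30-99 triggers no confirming test, so loss of CR can go unconfirmed without any retreatment. The same holds for a count of at least 30 but below twice baseline. This stands, and a retreatment rule does not repair it.

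**Other readings do not close the gap.** Using the Synopsis remark on follow-up length as a scoring rule would ignore the repeat course and give the same result. LOCF (Section 10.3.6) could carry a low count into a missing confirming test, but the plan does not say so, and it would not help where a rebounded count was obtained.

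**Conclusion.** The gap is confirmed. For a responder retreated before loss is confirmed and without bleeding, the text as written gives no loss and lets duration of R continue on the second course. Loss is biased down and the duration curve up. Each such patient is worth about 3-4 percentage points of loss of R, assuming the planning response rate of 78% and 29-40 analysed patients. How many there would be is unknown.

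The documents do not support saying that every retreated relapse is missed: bleeding, or a second low count, is scored as loss. Nor do they support saying that the whole period for observing loss coincides with the repeat-course window, since Visit 6 falls mostly after Day 28. The endpoints are secondary and not powered, and the non-inferiority conclusion in Section 10.3.7 rests on R alone. Whether counts after a repeat course can establish R is a separate question. This point should be corrected before analysis, but it does not alter the sample size or the primary test.

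**What to change.** In Sections 8.2 and 10.3.3, state for the main analysis that:

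- the start of a repeat course after R counts as loss of R, and as loss of CR for a patient in CR;
- the loss is dated at the unconfirmed low count that prompted the course or, if there was none, at the first repeat infusion;
- duration ends on that date as an event.

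Add a sensitivity analysis that censors at the first repeat infusion, and list the recorded reason for each repeat course.

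The downside is that a repeat course given for a reason other than a failing response would count as loss in the main analysis. The sensitivity analysis and the listing would show how much that matters.

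The cost is a few sentences and one extra analysis. Infusion times are already recorded (Sections 4.3, 6.2 and 7.4). The documents do not say that the reason for a repeat course is captured, so one eCRF field may be needed. The approach matches how a steroid increase is already treated. The rule on whether or when a repeat course is given is unchanged.
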